**Section 3 (to be completed at 1 Month visit)**

**1. Wound pain**

- 1) Please evaluate the pain you are **now** experiencing in the area of your wound by indicating on the 100-mm line scale below with “no pain” at the left end (0 mm) and “excruciating pain” at the right” end (100 mm)

**2. Satisfaction/Preference**

- 2) My overall experience with the wound closure is best described as
- Very satisfied
  - Satisfied
  - Dissatisfied
  - Very dissatisfied
- 3) I would recommend this type of wound closure to a friend or relative
- Yes    No

---

2 ABBREVIATIONS

Abbreviation	Explanation
ADE	Adverse Device Effect
AE	Adverse event
CDC	Center for Disease Control and Prevention
CI	Confidence interval
CIR	(Crude) Incidence rate
CMH	Cochran-Mantel-Haenszel
ED	Early Discontinuation
FAS	Full Analysis Set
FM	Farrington-Manning
ICTR	Integrated clinical trial report
IMD	Investigational medical device
N	Number of subjects in population
Max	Maximum
MLE	Maximum-Likelihood Estimate
MedDRA	Medical Dictionary for Regulatory Activities
mHCS	Modified Hollander Cosmesis Scale
Min	Minimum
Q1	First quartile
POSAS	Patient and Observer Scar Assessment Scale
PPS	Per Protocol Set
Q3	Third quartile
SAE	Serious adverse event
SAF	Safety Set
SAP	Statistical analysis plan
SAS	Statistical analysis software
SD	Standard deviation
TEAE	Treatment emergent adverse event
WHO-DD	World Health Organization Drug Dictionary

Système International d'Unités units are not included in this list.

3 INTRODUCTION

This statistical analysis plan (SAP) includes all definitions and analysis details for the analysis of the trial in accordance with the protocol dated 16 Jul 2018. The analysis will be performed by a contract research organization in accordance with this SAP.

4 TRIAL OBJECTIVES AND ENDPOINTS

Objectives	Endpoints

Primary Efficacy Objective:
 
 To compare the dehiscence rate between MAR-CUTIS and Dermabond Advanced between Day 1 and Day 10. 	
Primary Efficacy Endpoint:
 
 Total dehiscence rate of target incision/laceration assessed at the Day 10 visit.

Main safety objective:
 
 To compare the incidence of Adverse Events (AEs) between MAR-CUTIS and Dermabond Advanced. 	
Main safety endpoint:
 
 Adverse events within 1 month after treatment classified by severity and relatedness to the treatment.
Secondary	

 To compare the dehiscence rate between MAR-CUTIS and Dermabond Advanced at the Month 1 visit. 	
 Total dehiscence rate of target incision/laceration assessed at the Month 1 visit.

 To compare the incidence of AEs between MAR-CUTIS and Dermabond Advanced at additional study timepoints. 	
 Adverse events classified by severity and relatedness to the treatment.

 To evaluate the subject satisfaction with the cosmetic outcome after treatment of the surgical incision/laceration with MAR-CUTIS versus Dermabond Advanced 	
 Subject completed Patient and Observer Scar Assessment Scale (POSAS) done at the Month 1 and Month 3 visits.

 To compare the wound infection incidence between both treatment groups. 	
 Wound infection incidence assessed at the Day 10, Month 1, and Month 3 visits (diagnosed according to the Centers for Disease Control and Prevention [CDC] criteria for surgical site infection [See Protocol Section Error! Reference source not found. for more details]). Wound infection assessed on a binary scale (“1 - yes” or “0 - no”) for the following criteria: 
 Presence of erythema Presence of edema Presence of pain at rest Presence of elevated temperature A total score will be calculated for each subject.


 To evaluate the medical practitioner satisfaction with the cosmetic outcome after the closure of the target surgical incision/laceration with MAR-CUTIS versus Dermabond Advanced. 	
 Investigator completed POSAS done at the Month 1 and Month 3 visits. Investigator completed Modified Hollander Cosmesis Scale (mHCS) done at the Day 10 and Month 1 visits.

 To evaluate the subject comfort with the device during and after treatment with MAR-CUTIS versus Dermabond Advanced. 	
 A questionnaire related to subject experience and satisfaction with the device completed at the Day 10 and Month 1 visits.

 To evaluate the medical practitioner overall satisfaction and ease of use with the device during and after the closure of the target surgical incision/laceration with MAR-CUTIS or Dermabond Advanced. 	
 A questionnaire for investigators completed at the Month 1 visit.

[figure not shown]
5 TRIAL DESIGN

5.1 Overall trial design and plan

Only a brief synopsis of the trial design is presented here; full details can be found in the trial protocol.

This is a randomized, open-label, multicenter, comparator-controlled clinical study to compare MAR-CUTIS with Dermabond Advanced in closure of surgical incisions and lacerations ≤ 15 cm. A total of 189 subjects will be treated (defined as study product applied to the wound). Only subjects that are withdrawn from the study due to product failure at the time of application will be replaced. Subjects will be randomized 2:1 to MAR-CUTIS or Dermabond Advanced. Screening and baseline (randomization) can occur on the same day. Application of the investigational medical device (IMD) occurs on Day 0 (D0) with wound evaluation occurring on Day 1 (D1), Day 10 (D10), Month 1, and Month 3. Training on the application of both devices will be provided. An overview of the study design is shown in Figure 1.

Figure 1: Study design

The Study Procedures are described in Protocol Section 7.1.2.

5.2 Sample size

Assuming a dehiscence rates of 3.05% for MAR-CUTIS and 0.85% for Dermabond Advanced, 189 subjects (2:1, 126 MAR-CUTIS vs 63 Dermabond Advanced) ensure a power of 85% to show noninferiority of MAR-CUTIS compared with Dermabond Advanced using a one-sided significance level of $\alpha = 0.05$ and a FM test given a noninferiority margin of 8%.

The assumed dehiscence rates of 3.05% and 0.85% were derived based on the assumption to have 15% of subjects in the trial with lacerations that have a dehiscence rate of 0.5% for MAR-CUTIS and 0% for Dermabond Advanced and 85% of subjects in the trial with incisions, with dehiscence rates of 3.5% for MAR-CUTIS and 1% for Dermabond Advanced.

The assumed noninferiority margin of 8% is based on an average of dehiscence rates observed in previous studies, e.g. [Siddiqui et al. \(2013\)](#); dehiscence between 2%-13%), [Muncie et al. \(2018\)](#); dehiscence rates between 0.8-7.5%) and [Eymann et al. \(2010\)](#); dehiscence rates between 2%-24%). Noninferiority versus a placebo would not be ethical in the context of this trial, and thus has been set conservatively versus an approved IMD (Dermabond).

5.3 Randomization

Subjects (ie, the unique subject identifier [ID] consisting of center ID and subject ID) will be randomly allocated to treatment according to a randomization scheme designed using the covariate-adjusted dynamic allocation method as implemented in Balance ([Medidata, 2015](#)). The algorithm combines complete randomness with a minimization method ([Pocock and Simon, 1975](#)), not only looking at marginal balances, but also considering the treatment balances overall and within individual strata, to ensure a balanced treatment allocation. Based on the expected clinical relevance of the explanatory variables for incision and laceration closure, the algorithm is implemented by assigning a different weight to the stratification factors to be included in the trial and minimize unbalances (i.e., wound type having more importance than the other two factors, and age group having more importance than skin type). Further details regarding the parameters used to implement the randomization in Balance are documented in the form “Balance Study Configuration Requirements”.

The incision/laceration will be prepared for closure as per the standard of care at a treating hospital. The treating physician will assess the need and perform closure of deep tissue layers as necessary before proceeding with the randomization and subsequently with the closure of the last (dermal) layer with the IMD.

Eligible subjects will be randomized 2:1 to MAR-CUTIS or Dermabond Advanced.

The study will include 3 levels of stratification as randomization factors:

- By wound type (lacerations and incisions)
- By skin type according to the Fitzpatrick classification (types I to III vs. types IV to VI)
- By age group (aged 2 to 21 years and ≥ 22 years)

Additionally, center will be considered as a further randomization factor as recommended by ICH E9.

6 OVERVIEW OF PLANNED ANALYSES

6.1 Final analysis

The final analysis will be performed after all subjects have completed the trial, and the data has been hard locked. The results of the final analysis will be the basis for the integrated clinical trial report (ICTR).

7 DOCUMENT AND CHANGE HISTORY

7.1 Changes in analysis compared to the trial protocol

Change from protocol	Rationale for change
Determination of Sample Size	The assumed dehiscence rates for the determination of sample size have been described more clearly. Moreover, the text has been revised, and further information about the choice of the assumed dehiscence rates and noninferiority margin were added. These changes will be implemented in the upcoming protocol amendment.
Randomization	Additional text was added in Section 5.3 to clarify the setting up of the dynamic allocation, and preparation of the subject before randomization.
Adding center as randomization factor	Although not specifically mentioned in the protocol, center has been added in the randomization process as recommended by ICH E9. This change will be implemented in the upcoming protocol amendment.
Per Protocol Set (PPS)	The PPS was added in Section 9.5 to perform a sensitivity analysis of the primary efficacy. This change will be implemented in the upcoming protocol amendment.

8 ANALYSIS CONVENTIONS

8.1 General principles

If two of the analysis sets as defined in the SAP coincide, presentations will only be prepared for one analysis set.

All presentations will be done by treatment group and overall, and by visit where applicable.

The data collected and derived in the trial will be presented in subject data listings sorted by subject number and treatment.

Data collected in this trial will be summarized according to their nature as follows:

- Continuous variables: number of non-missing observations, arithmetic mean, standard deviation (SD), minimum (Min) and maximum (Max) values, median, and first (Q1) and third (Q3) quartiles. If there are less than 5 observations, descriptive statistics will be presented based on the rules specified in Section 16.1.1.2.
- Categorical variables: absolute and relative frequencies. If not defined otherwise, the percentage denominator will be the number of subjects still in the trial (including missing values) at the respective time point in the analysis set. The category missing will only be displayed if missing values occur. Categories with a frequency of 0 will not be presented if not otherwise specified.

Medical terms (e.g., prior and concomitant diseases, adverse events) will be coded via Medical Dictionary for Regulatory Activities (MedDRA) version 21.0 or latest version before the database is locked. For the analysis, the primary System Organ Class (SOC) will be used. Medications will be coded according to World Health Organization Drug Dictionary (WHO-DD) version March 2018 or latest version before the database is locked.

Shells for summary tables, subject listings, and figures are described in a separate document, which is included as an Appendix to the SAP. Templates for each unique table, listing, and figure are provided. These provide only a draft indication of the content and appearance of the tables, listings, and figures, and the final output may vary in appearance from these templates.

All statistical analyses will be performed using SAS statistical software version 9.4 or higher (SAS Institute, Cary, NC).

[Table 1](#) shows the use of analysis sets in different analyses as defined in Section 9.

Table 1: Use of analysis sets

	Enrolled Set	Allocated Set	SAF	FAS
Subject disposition	X	X		
Discontinuations			X	
Protocol deviations			X	
Demographics			X	X
Other baseline characteristics			X	X
Subject medical history			X	
Previous and concomitant medication			X	
Exposure			X	
Compliance			X	
Primary endpoint			X	X
Secondary endpoints				
Secondary efficacy endpoints			X	X
Wound infection			X	X
Adverse events	X		X	
Laboratory values			X	
Other safety assessments			X	

FAS = Full Analysis Set, SAF = Safety Analysis Set

8.2 Definitions

8.2.1 Definition of subgroups

For selected outcomes (specified in the following sections), descriptive statistics will be summarized for the following subgroups: type of wound (incision/laceration), skin type (Fitzpatrick skin types I to III/types IV to VI) and age group (pediatric 2 to <22 years/adult ≥22 years).

8.2.2 Further definitions

Baseline	Baseline is defined as the last observation (scheduled or unscheduled) before application of the IMD (i.e., D0), if not otherwise specified.
----------	--

Investigational Medical Devices (IMD)	- MAR-CUTIS: a polyurethane-based skin adhesive, used for topical closure of incisions and surgical wounds replacing the last dermal suture line. - Dermabond Advanced: a topical skin adhesive used to hold closed easily approximated skin edges of wounds from surgical incisions, and simple, thoroughly cleansed, trauma-induced lacerations.
On-treatment-period	After the start of the application of the IMD (D0) until the end-of-treatment visit (Month 3).
Pre-treatment-period	Before the start of the application of the IMD, i.e. D-21 to D0.
Trial completers	Trial completers will complete the screening-presurgical examination visit (Day -21 to D0), the D0 visit, and at least the Month 3 follow-up visit.

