## 6 STUDY OBJECTIVES

Objectives	Endpoints

Primary Efficacy Objective:
 
 
To compare the dehiscence rate between MAR-CUTIS and Dermabond Advanced between Day 1 and Day 10.
 
	
Primary Efficacy Endpoint:
 
 
Total dehiscence rate of target incision/laceration assessed at the Day 10 visit.
 

Main safety objective:
 
 
To compare the incidence of AEs between MAR-CUTIS and Dermabond Advanced.
 
	
Main safety endpoint:
 
 
Adverse events within 1 month after treatment classified by severity and relatedness to the treatment.
 

Secondary
	

 
To compare the dehiscence rate between MAR-CUTIS and Dermabond Advanced at the Month 1 visit.
 
	
 
Total dehiscence rate of target incision/laceration assessed at the Month 1 or Early Discontinuation visit (if Early Discontinuation occurs before Month 1).
 

 
To compare the incidence of AEs between MAR-CUTIS and Dermabond Advanced at additional study time points.
 
	
 
Adverse events classified by severity and relatedness to the treatment.
 

 
To evaluate the subject satisfaction with the cosmetic outcome after treatment of the surgical incision/laceration with MAR-CUTIS versus Dermabond Advanced.
 
	
 
Subject-completed Patient and Observer Scar Assessment Scale (POSAS) done at the Month 1 and Month 3 visits or at the Early Discontinuation visit (if Early Discontinuation occurs before Month 1).
 

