14.1 Adverse events

A treatment emergent adverse event (TEAE) is defined as any adverse event that, based on start date information, occurs in the on-treatment-period as defined in Section 8.2.2. This includes any events related to the procedures, the IMD, or the comparator.

A pre-treatment non-TEAE is an adverse event starting in the pre-treatment period as defined in Section 8.2.2.

A serious adverse event (SAE) is any untoward medical occurrence of effect that:

- Led to death, or
- Led to serious deterioration in the health of the subject, or
- Led to fetal distress, fetal death, or a congenital abnormality or birth defect.

This includes device deficiencies that might have led to a SAE. More details on the definition of SAEs are available in Protocol Section 9.3.1.

If there are partial dates or times, an adverse event will be considered treatment emergent unless the information available will clearly exclude it. Further details can be found in Section 16.1.4.1.

Assignment of TEAEs to treatment will be based on the definition of the on-treatment-period given in Section 8.2.2, thus, TEAEs occurring during the on-treatment period are assigned to the respective treatment.

The causal relationship of TEAEs to IMD is categorized as follows:

Category	Assessment by investigator
Related	probable certain/very likely possible
Not related	unlikely unrelated

An Adverse Device Effect (ADE) is an AE related to the use of an IMD. This includes any AE resulting from insufficiencies or inadequacies in the instructions for use, deployment, implantation, installation, operation or any malfunction of the IMD. ADEs are a subset of TEAEs.

An ADE that results in any of the consequences characteristic of a SAE will be considered as a serious ADE.

Serious ADEs which by its nature, incidence, severity or outcome have not been identified in the current version of the MAR-CUTIS risk analysis report or Instructions for use for Dermabond Advance (see Protocol Section 15.2 for more details) will be considered as unanticipated ADEs. Anticipated ADAs are defined as events that have been previously identified in applicable product information.

The following overview tables will be generated by treatment group and overall.

1. Summary of the number and percentage of subjects with at least 1 of the following events, and of summary of the number and percentage of TEAEs for:
 - TEAEs.
 - Serious TEAEs.
 - Non-serious TEAEs.
 - TEAEs leading to withdrawal from the trial.
 - ADEs.

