 - Serious ADEs.
 - ADEs leading to withdrawal from the trial.
 - Anticipated/Unanticipated ADEs
 - TEAEs/ADEs with fatal outcome.

The percentage denominator will be the number of subjects by treatment group in the SAF, or the number of TEAEs, respectively.

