14.1.1 Incidence, incidence rates and number of events

The incidence of an adverse event is defined as the number of subjects with occurrence of this adverse event during the period of interest.

The incidence rate (crude incidence rate [CIR]) of an adverse event is defined as the number of subjects with occurrence of this adverse event during the period of interest divided by the total number of subjects N in the respective group (e.g., treatment group).

The incidence, incidence rate, the number of events, and the percentage of events will be summarized by PT (sorted by decreasing incidence rate in the MAR-CUTIS treatment group) for:

- TEAEs.
- Serious TEAEs.
- Non-serious TEAEs.
- TEAEs leading to withdrawal from the trial.

- ADEs.
- Serious ADEs.
- ADEs leading to withdrawal from the trial.
- Anticipated/Unanticipated ADEs.

Percentages will be calculated related to the total number of subjects/events presented in the respective table e.g., for the presentation of PTs for serious TEAEs percentages will be related to the number of subjects with serious TEAE/the total number of serious TEAEs, respectively.

For serious TEAEs, percentages will additionally be presented related to the total number of all subjects/events, respectively.

All tables above will be presented only for incidence rates greater than or equal to 2% in any treatment group.

The incidence, incidence rate, the number of events and the percentage of events will be summarized by SOC and PT (sorted alphabetically) for each:

- TEAEs.
- Serious TEAEs
 - Fatal TEAEs.
- Non-serious TEAEs.
- TEAEs leading to withdrawal from the trial
- ADEs
- Serious ADEs
 - Fatal ADEs.
- ADEs leading to withdrawal from the trial.
- Anticipated/Unanticipated ADEs.

Percentages will be calculated related to the total number of subjects/events presented in the respective table e.g., for the presentation of SOC and PT for serious TEAEs percentages will be related to the number of subjects with serious TEAE/the total number of serious TEAEs, respectively.

For serious TEAEs, percentages will additionally be presented related to the total number of all subjects/events, respectively.

If more than 10% subjects are withdrawn from the trial due to TEAE, the incidence and the incidence rate of TEAEs leading to withdrawal from the trial will be summarized by SOC and PT.

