For all enrolled subjects, the incidence, incidence rate, the number of events and the percentage of events (related to the total number of events) will be summarized by SOC and PT (sorted alphabetically) for each:

- Pre-treatment non-TEAEs.
- Serious pre-treatment non-TEAEs.

Presentation will only be overall and not per treatment.

The number and percentage of events will be summarized by SOC and PT (sorted alphabetically) for the following TEAE / ADEs descriptors. Presentation will be for TEAEs / ADEs only:

- Intensity: mild, moderate, severe.
- Outcome: recovered, not yet recovered, recovered with sequelae, death, unknown.
- Action taken with the IMD: none, medication or therapy provided, IMD removed, concomitant medication changed, other.

Denominator for percentage calculation will be the number of all TEAEs / ADEs for presentation of overall SOCs, and the number of TEAEs/ADEs per SOC or PT respectively, for the presentation per SOC or PT, respectively.

Measures of location and variation will be calculated for:

- Duration of TEAEs.
- Time to onset of TEAEs.

The following listings will be produced for all enrolled subjects:

- Deaths.
- Serious adverse events other than death.
- Adverse events leading to withdrawal from the trial.

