16.1.1.9 Conversion of time intervals

If a time interval was calculated in minutes, hours or days and needs to be converted into months or years, the following conversion factors will be used:

- 1 month = 30 days.
- 1 year = 365.25 days.

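### The SAP specifies no 1-month adverse event analysis, although that is the main safety endpoint; its AE percentage rules conflict, and its infection incidence rule departs from the CDC diagnosis

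*SAP*

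**What the plan says.** **Window.** Protocol section 6 defines the main safety endpoint as "Adverse events within 1 month after treatment classified by severity and relatedness to the treatment", and SAP section 4 repeats it. AEs at further time points are a separate secondary objective. SAP 14.1 defines a treatment-emergent AE (TEAE) as "any adverse event that, based on start date information, occurs in the on-treatment-period as defined in Section 8.2.2", and SAP 8.2.2 gives that period as "After the start of the application of the IMD (D0) until the end-of-treatment visit (Month 3". For severity, outcome and action taken, SAP 14.1.1 states: "The number and percentage of events will be summarized by SOC and PT (sorted alphabetically) for the following TEAE / ADEs descriptors".

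**Denominators.** For the overview table, SAP 14.1 states: "The percentage denominator will be the number of subjects by treatment group in the SAF". SAP 14.1.1 defines the incidence rate as subjects with the event "divided by the total number of subjects N in the respective group". For the preferred-term and system-organ-class tables it then states: "Percentages will be calculated related to the total number of subjects/events presented in the respective table". A percentage on all subjects is added for serious TEAEs only.

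**Infection.** Protocol sections 6 and 9.3.6 define infection incidence by the CDC surgical site infection criteria and add a four-sign score. SAP 13.2.3 opens with the CDC diagnosis. SAP 13.2.3.1 then evaluates incidence through the presence of erythema, edema, pain at rest or raised temperature. SAP 14.3 repeats that analysis on the Safety Set.

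**The concern.** The main safety objective is to compare AE incidence between arms. Followed as written, the SAP serves the secondary objective (all events to Month 3) and never produces the main endpoint. Late events unrelated to the adhesive can dilute an early difference. If the 1-month cut is added only when tables are programmed, its window will be chosen after data exist in an open-label trial.

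Severity shown only as a percentage of events does not give the share of subjects affected, which is how SAP 14.1.1 itself defines incidence.

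Two percentage rules in one section can place figures pointing in opposite directions side by side.

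The infection error can run either way. If signs are recorded for every subject, local skin reactions count as infections. If they are recorded only once an infection has occurred, a CDC infection showing none of the four signs is missed.

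**Working it through.** The plan states no figure to reproduce here, so the check compares text and adds simple arithmetic.

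**1. Is there a 1-month cut anywhere in the SAP?**
- SAP 8.2.2 defines only a pre-treatment and an on-treatment period.
- The incidence definition in SAP 14.1.1 refers to a period that is never specified.
- SAP 16.1.4.1 assigns events to time periods but adds none.
- The time-to-onset summary does not give 1-month incidence.
- Protocol 10.1.4 defers detail to the SAP, and SAP 7.1 lists no change on this point.
- The table shells are a separate document and were not available, so the finding concerns the SAP text.

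**2. Length of the window.** SAP 16.1.1.9 sets "1 month = 30 days". Month 3 is taken as Day 90, with the ±14-day visit window in Protocol 7.1.2:
- (90 − 14)/30 = 76/30 = 2.53
- (90 + 14)/30 = 104/30 = 3.47

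**3. Dilution (assumed figures; the documents give none).** Take 1-month incidence of 20% vs 10%, ratio 2.0. Let a share x of the still unaffected subjects in both arms have a first AE later. Month 3 incidence is then 0.20 + 0.80x vs 0.10 + 0.90x.

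| x | Month 3 incidence | Ratio | Difference |
|---|---|---|---|
| 5% | 24.0% vs 14.5% | 1.66 | 9.5 points |
| 10% | 28% vs 19% | 1.47 | 9.0 points |
| 20% | 36% vs 28% | 1.29 | 8.0 points |

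**4. Severity by events (assumed counts, one event per subject).** Suppose 8 of 40 events are severe among 126 subjects, and 2 of 10 among 63. By events, both arms show 20%. By subjects, the figures are 8/126 = 6.3% and 2/63 = 3.2%.

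**5. Denominators (planned arm sizes 126 and 63; assumed counts).** Suppose adverse device effects occur in 12 and 3 subjects, and one term in 6 and 2 of them.
- On arm size: 6/126 = 4.8% vs 2/63 = 3.2%.
- On subjects in the table: 6/12 = 50% vs 2/3 = 67%.

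The order of the arms reverses. Only serious TEAEs are promised the all-subject percentage as well. Adverse device effects, serious device effects and events leading to withdrawal are not.

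**6. Infection rule against the CDC criteria in Protocol 15.1.**
- The signs are not sufficient: redness, warmth or swelling treated as cellulitis does not by itself meet criterion d for a superficial infection.
- They are not necessary: purulent drainage from the superficial incision meets criterion a without any of the four.
- When signs are recorded is unclear. The schedule in Protocol 7.1.2 lists infection evaluation without condition, while 8.2.2 to 8.2.4 make it conditional on an infection. No size is therefore given.

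**The case against.** **The window may be handled elsewhere.** The shells could contain a 1-month table, and every 1-month event is included in the Month 3 tables. The first point is a real limit on what can be said. However, SAP section 3 says the SAP holds all definitions and analysis details, and SAP 8.1 describes the shells as only a draft indication. Inclusion in a longer window does not report the shorter one.

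**The dilution figures are assumed, and the ratio flatters them.** True: the difference falls only from 10 points to between 9.5 and 8.0. No safety test is planned, so no formal inference changes.

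**Severity by events fits the endpoint's wording.** It does. The case for subject counts rests on the objective, which concerns incidence. Relatedness is already given by subject through the device-effect tables, though over the longer window.

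**The 30-day cut is a choice.** SAP 16.1.1.9 is a conversion rule, and the endpoint could also mean up to the Month 1 visit (±7 days). Applying the SAP's conversion to an onset interval is consistent with it, but the choice must be written down.

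**The incidence rate is always specified, so the other percentage is only an extra.** This narrows the harm to contradictory figures side by side. It does not remove it.

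**The infection section opens with the CDC diagnosis, so the signs may only describe diagnosed infections.** That reading is possible, but it is not what 13.2.3.1 says. It also stands that the appended CDC criteria refer to operative procedures, while about 40 lacerations are planned, and that superficial infections are followed for only 30 days. Tabulating the CDC diagnosis does not settle those two points.

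**Conclusion.** The concern holds on all three parts, as a matter of the SAP text. The named main safety endpoint has no specified analysis. The AE tables cover 2.5 to 3.5 times its window, taking a month as 30 days and Month 3 as Day 90 ± 14 days. On the assumed incidences, a ratio of 2.0 would appear as 1.66 to 1.29. Subject percentages follow two rules that can reverse the arms, as the assumed counts show. The infection rule contradicts both its own parent section and the protocol, in a direction that depends on when signs are recorded.

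The consequence is confined to descriptive safety and infection reporting. The primary test, its alpha and its power are not touched. The SAP should be corrected, but the trial's main conclusion does not depend on it.

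**What to change.** 1. **SAP 14.1 and 14.1.1:** add overview and by-term TEAE and device-effect tables by severity and relatedness, counting subjects as well as events. Restrict them to an onset date minus application date of at most 30 days. Use the date difference and not the trial-day variable, because SAP 16.1.1.4 adds 1 from Day 0 onward. Label these tables as the main safety endpoint and keep the Month 3 tables as secondary.
2. **SAP 14.1.1:** delete the in-table denominator for subject percentages. Use the Safety Set size per treatment group throughout the post-application TEAE and device-effect tables. The pre-treatment tables on enrolled subjects keep their own denominator.
3. **SAP 13.2.3.1:** tabulate the CDC-based diagnosis (yes/no) as infection incidence and keep the four signs for the score in 13.2.3.2. State how the diagnosis is applied to lacerations and at Month 3.

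The cost is SAP wording and a few extra tables. Onset dates, severity, causality and the CDC-based diagnosis are already collected.
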